7. Walking >30 min continuously daily or participating in a regular (more than twice a week) exercise program
8. Past participation in a CBT program
9. Inability to walk unaided as this is necessary for some of the physical testings
10. Grade IV on Kellgren and Lawrence grading system for Osteoarthritis classification
11. Medical condition precluding safe exercise such as uncontrolled hypertension or heart condition
12. Major joint pain (e.g. back, hip or ankle) to a greater extent than the knee pain that could limit the ability to exercise
13. Self-reported psychiatric history such as schizophrenia, epilepsy and bipolar disorders
14. Self-reported diagnosis of current clinical depression
15. Neurological condition such as Parkinson's disease, Multiple sclerosis or stroke
16. Inadequate written and spoken Arabic
17. Unable to comply with the protocol such as the inability to attend therapy sessions or attend assessment appointments at the health center.

- **Sample Size**

Convenient sampling has been used for this study based on the time and resources limit for this study. A number of twenty participants were assigned in each group.

c. Study Procedure

Eligible patients will be randomly allocated to either the study group or the control group (1:1). Initial assessments by self-reported questionnaires will be done at baseline. Initial assessment of knee joint will be done as well as the objective outcome measures that include: Isometric muscle strength of quadriceps using a hand-held dynamometer, functional tests (40mFPWT/ 30s CST/ 9 SST). The total time for completion of the three tasks will be approximately 25 min (Rejeski et al., 1995). Then the participant will be prescribed strengthening exercises under the supervision of the researcher and to follow at home, 3-4 times per week. Depending on the participant's allocation, the participant will be provided with a link to access online material of pre-recorded sessions of CBT or educational material about knee pain, healthy diet and other general information. In addition to their access to iCBT sessions, the study group will be able to access the same educational material that is accessed by the control group. On the 2nd -8th session, the physiotherapist will follow up on the exercises and progress as needed and will respond to any questions or doubts the participant has regarding the online sessions.

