In the 8th session, self-reported questionnaires will be undertaken again as well as the objective outcome measures. All self-reported questionnaires will be completed through a survey administration application (Google or Microsoft forms) except for the questionnaires required for eligibility i.e. PHQ-2, K6 and KOOS-PS. All participants will provide written informed consent prior to their enrolment.

d. Interventions

1. Standardized Exercise Program (common to both groups)

Participants will attend the clinic for 8 supervised physiotherapy sessions designed to strengthen lower limb muscles. Eight sessions were chosen as this number should be able to achieve improvements in pain and function (Fransen et al., 2015).

The exercise program will be adopted from Bennell et al. (2012) study as it proved its effectiveness in improving pain and function. The program will comprise of a minimum of 4 and a maximum of 6 individualized lower limb exercises to be performed 3-4 times per week. All exercise programs will include at least 3 knee extensor strengthening exercises, and at least 1 hip abductor strengthening exercise selected from a pre-determined list (Table 1). The remaining optional 1 or 2 exercises can be chosen from other exercises on the list or be any exercise of the researcher's choice, in order to address an impairment or functional deficit related to the participant's knee problem. Examples include functional drill or dynamic balance exercise(s), muscle stretch(es) or other lower limb muscle strengthening. The researcher will select exercises and prescribe dosages for each exercise based on the assessment findings, including muscle strength, the participant's pain and their perceived level of effort during the performance of the exercise. Participants might be asked to have elastic bands and/or ankle cuff weights for the execution of the exercises if required. Participants will be asked to follow exercises at home 3-4 times/week.

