A brief assessment will be performed by the researcher at each physiotherapy session in order to ascertain any adverse effects (if any) that may have occurred with home exercises and to check the quality and form of exercise performance. Progression of exercises is an essential component of the program and the findings from the assessment will help guide the researcher's decisions regarding progression. Progression will be provided by varying the exercises including the type of exercise as well as the number of repetitions, load or degree of difficulty within an exercise. In order to gain strength, the level of effort experienced during each strengthening exercise will be self-rated as at least 5 out of 10 (hard) on a modified Borg Rating of Perceived Exertion (RPE) CR10 scale designed specifically for strengthening exercise (Appendix 1)(Day et al., 2004). In addition, the resistance prescribed will aim to approximate a 10-repetition maximum level. Participants will be provided with exercises handouts and log sheets (Appendices 2 and 3).

The researcher will also discuss the disease-specific and general health benefits of increased levels of general physical activity, including both incidental physical and whole-body exercise.

Risk Factor

Some discomfort is expected during the strengthening exercise sessions and whole-body physical activity, however, the pain should subside to usual levels by the next day with no increase in swelling following the exercise session. Participants will be taught how to determine whether pain levels during and for a short time after the exercises are acceptable. If a specific exercise is aggravating the participant's pain, then the researcher will reduce the resistance, dosage and/or level of challenge within the exercise until the pain flare settles. Progression will be partially based on the absence of significant pain (2-3 out of 10) during exercises (Crossley et al., 2019).

2. Educational Material (common to both groups)

Participants will receive a specific link to access online educational material about chronic knee pain. This will be 5 sessions, with each lasting for 10-15 minutes, and will comprise of general information about the following: healthy eating, water intake, physical activity, emotions and proper footwear. Participants are encouraged to access the education material at their own leisure and pace.

3. Internet-Based Cognitive Behavioural Therapy (study group only)

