In addition to their access to the educational material, participants in this group will receive a link to access pre-recorded online sessions of CBT. The content of sessions will be adopted from the painCOACH program that was effectively used in an RCT for the effects of adding and iCBT to an exercise program in persistent hip pain patients (Bennell et al., 2015). The iCBT translated key therapeutic components of face-to-face PCST (keefe et al., 2002). The program proved its effectiveness in improving pain and function in patients with arthritis (Bennell et al., 2018; Rini et al., 2015).

The link will contain eight 35- to 45-minute sessions, designed to be completed weekly, each will provide an explanation of a cognitive or behavioural pain coping skill. Session 1 will provide an overview, including a therapeutic rationale of CBT, followed by training in progressive muscle relaxation. Sessions 2 through 7 will teach brief relaxation skills, activity-rest cycling, pleasant activity scheduling, cognitive restructuring, pleasant imagery, and problem-solving. Session 8 will consolidate learning and teaches strategies for long-term skill use. Each session has to be completed within the same week where the physiotherapy session is given.

Participants will be asked to practice and actively use each new skill they learn, and skills practice will be reviewed in subsequent sessions. Participants will have the opportunity to ask questions when they attend the physiotherapy exercise session. Companion worksheets and practice logs will be provided.

e. Outcome Measures

1. Primary Outcome Measures

- The Single-Item Numerical Rating Scale (NRS)

Participants will be asked to rate their average knee pain in the past week on a scale from 0 to 10, with '0' meaning 'No pain' and '10' meaning 'Pain as bad as you can imagine'(Dworkin et al., 2005). This is a reliable tool that was recommended by the Veterans health administration workgroup as one of the core outcome measures for chronic musculoskeletal conditions (Kroenke et al., 2019).

- 40-m Fast-Paced Walk Test (40-m FPWT)

A participant will be instructed to walk as quickly but as safely as possible to a mark 10 m away, return, and repeat for a total distance of 40 m. Regular walking aid is allowed and recorded. Time of one trial, with turn time excluded, is recorded and expressed as speed m/s by dividing distance (40 m) by time (s) (Dobson et al., 2013).

- Step Test (ST)

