This research was approved by 1. The Scientific Research and Publication Committee, College of Health and Sport Sciences (CHSS), University of Bahrain (CHSS SRPC Recommendation No: 6/2020-21 dt. Feb 23, 2021) 2. Research Technical Support Team, Office of Assistant Undersecretary for Researches and Services, Ministry of Health, Kingdom of Bahrain, Project ID: 498 dt. Apr 8, 2021.

- Human Participants

Participants will take part in the study voluntarily after receiving sufficient information and after signing a consent sheet. Moreover, participants will have the right to withdraw from the study at any stage if they wish to do so without prejudice.

- Personal Data

Personal information of participants will be dealt with confidentiality and will not be shared with anyone. Research information will be kept safely in a USB flash drive. Only research personnel will have access to the files. After completion of this study, the personal and contact details of participants will be erased while the dataset will be retained and might be used for further researches done by the UOB or the MOH in the kingdom of Bahrain.

- Anonymity of Participants

The anonymity of participants will be ensured by assigning each participant a code number to enter and to analyse the primary data collected from questionnaires or physical assessments. Participant's face or identity will not be revealed if photographs or video recordings were taken.

- Conflict of Interest

The researcher declares that she has no conflict of interest.

h. Data Analysis

Main comparative analyses between groups will be performed using intention-to-treat. This analysis will include all participants who have missing data and those who do not fully adhere to the protocol. Demographic characteristics, as well as baseline scores on primary and secondary outcome measures, will be inspected to assess baseline comparability of treatment groups. These variables will also be examined for those participants who withdraw from the study and those who remain. Descriptive statistics will be presented for each group as the mean change (standard deviation, 95% confidence intervals) in the outcomes from baseline to each time-

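### Adverse effects are sought only for home exercises, which both arms do, and are not reported by arm, so evidence on harms of iCBT is limited to mean changes on the efficacy scales

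*Combined protocol and SAP*

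**What the plan says.** Section d describes three components. The exercise programme and the educational material go to both groups; iCBT goes to the study group only.

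The adverse-effect enquiry sits under the exercise programme. At each physiotherapy session the researcher makes a brief assessment "in order to ascertain any adverse effects (if any) that may have occurred with home exercises", and its findings help to guide progression of the exercises. The Risk Factor paragraph adds that "Some discomfort is expected during the strengthening exercise sessions and whole-body physical activity" and describes how pain flares are handled. It does not describe recording them as data.

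The iCBT consists of eight weekly sessions of 35 to 45 minutes. "Participants will be asked to practice and actively use each new skill they learn", and their practice is reviewed in later sessions. Under section c, at sessions 2 to 8 the physiotherapist "will respond to any questions or doubts the participant has regarding the online sessions". No enquiry about adverse effects is attached to iCBT.

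Adverse events are not among the primary or secondary outcomes in section e. Section h states: "Descriptive statistics will be presented for each group as the mean change (standard deviation, 95% confidence intervals) in the outcomes". It then plans baseline-adjusted comparisons of mean change, proportional odds models for improvement and MCID attainment, and a description of those who withdraw against those who remain.

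**The concern.** The only targeted question about harm concerns a component that randomisation does not vary. Nothing systematic is asked about the component that it does vary, in participants selected for a PHQ-2 score of at least 2 and a K6 score of at least 7. Someone upset by an iCBT session, or worse for some weeks and then recovered, falls outside the stated question. So does someone who leaves because of the programme.

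The Expected outcomes section hopes that the results will identify who benefits most and may reshape selection for such programmes. A recommendation of that kind needs some account of harm alongside benefit. If harms of iCBT are not asked about, their absence from a report would carry little information. Events that are merely volunteered could also be noted unevenly between arms: the Limitations section says that one researcher conducts the study and that this carries a risk of bias.

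**Working it through.** The plan gives no figure for adverse events to reproduce. The 20 participants per group (section b, Sample Size) were set by convenience, with no alpha, power, event rate or SD behind them. Everything below marked as assumed is an assumption.

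**1. Which components the enquiry covers**

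- Home exercise: both arms; asked about at each session.
- Supervised exercise: both arms; discomfort is managed, with no recording described.
- Education: both arms; adverse effects not asked about.
- iCBT: study group only; adverse effects not asked about. Contact consists of answers to participants' questions and review of skills practice.

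**2. What the planned outcomes can show**

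Pain NRS, PHQ-9, K6, KOOS-PS, SF-12 and the functional tests are measured in both arms at 0 and 8 weeks, and their changes are compared in either direction. With n = 20 per arm, assumed two-sided alpha 0.05, 80% power and assumed baseline correlation ρ, the detectable standardised difference is

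(1.960 + 0.842) × √(1 − ρ²) × √(2/20).

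- ρ = 0: 2.802 × 1 × 0.316 = 0.89 SD
- ρ = 0.7: 2.802 × 0.714 × 0.316 = 0.63 SD

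A large average worsening on iCBT could therefore be detected.

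**3. What they would miss**

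- *Individual deterioration.* Suppose 10% of the iCBT arm, 2 of 20, are harmed and the others are unaffected. For those two alone to move the arm mean by 0.63 SD, each would have to worsen by 0.63 × 20 / 2 = 6.3 SD. The proportional odds models are framed around improvement and MCID attainment. Perceived change might register worsening, but section e lists no instrument for it.
- *Transient distress.* According to section e, K6 covers the most recent 4 weeks and the pain NRS the past week. At week 8, distress confined to roughly the first four weeks lies outside both windows.
- *Withdrawal because of iCBT.* The final questionnaires are completed in the 8th session, so a person who has left may have no week-8 score. Section h compares the characteristics of withdrawers with those of participants who remain, but mentions neither reasons nor arm.

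**4. What a question put to everyone could show at 20 per arm**

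P(at least one event among 20) = 1 − (1 − p)^20, with p the assumed true rate:

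- p = 1%: 1 − 0.99^20 = 0.18
- p = 5%: 1 − 0.95^20 = 0.64
- p = 10%: 1 − 0.90^20 = 0.88

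These are chances that an event occurs; it is seen only if the question elicits it. With 0 of 20, the one-sided 95% upper limit is 1 − 0.05^(1/20) = 0.139, about 14%.

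**5. Whether a between-arm test would be worthwhile**

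Power of Fisher's exact test at 20 per arm (two-sided 0.05, assumed rates, control vs iCBT):

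- 5% vs 15%: 7%
- 5% vs 20%: 17%
- 5% vs 30%: 45%
- 0% vs 30%: 76%

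With no control events, the smallest significant split is 0 vs 5 (p = 0.047). By the normal approximation, 80% power needs 141 per arm for 5% vs 15% and 76 per arm for 5% vs 20%. A significance test would have little value.

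**The case against.** The strongest reply is that mood, distress, pain and function are already measured in both arms and compared without regard to direction. Worsening mood on iCBT is what PHQ-9 and K6 would pick up. This stands, and it limits the point. A reader might infer that the trial cannot show whether iCBT causes harm; the documents do not support that, because average worsening would appear in the planned comparisons. It does not answer the gaps in timing, in individual deterioration and in withdrawal.

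A reader might also infer that iCBT is given without any guidance to a highly vulnerable group. That is not supported either. The physiotherapist answers questions about the online sessions, skills practice is reviewed, and exclusions 13 and 14 remove self-reported psychiatric history and current clinical depression. None of this is an enquiry about harm, but it is contact and it is selection.

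It can be said that an event table at 20 per arm would settle nothing. For a between-arm test that is true, as the power figures show. It is no argument against asking: an upper limit of about 14% from 0 of 20 has a meaning only if the question was put.

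Finally, the protocol makes no safety claim, so a misleading statement about harm would belong to a later report. That is fair, and it is one reason for treating the matter as an improvement and not as a defect in the efficacy comparison.

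**Conclusion.** The point holds in this form: adverse effects are sought only for a component common to both arms and are not reported by arm, so evidence on harms of iCBT is limited to mean changes on the efficacy scales at 0 and 8 weeks. Discrete, transient or individual deterioration, and withdrawal because of iCBT, would be missed.

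This is a cheap improvement. It contradicts no figure in the plan and leaves the primary comparisons as they are. The existing scales have 80% power only for average differences of about 0.63 to 0.89 SD, which rests on an assumed two-sided alpha of 0.05 and baseline correlations of 0.7 to 0. Wider enquiry would give descriptive evidence only; the 18% to 88% range depends entirely on assumed event rates of 1% to 10%.

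**What to change.** Keep the home-exercise check as it is, because it guides progression. Add to it:

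- At sessions 2 to 8, in both arms, one neutral scripted question on any new or worse symptom, physical or emotional, since the last visit. Record onset, severity and whether treatment was stopped. Use identical wording in both arms and do not rely on the researcher's attribution to a component, since only one arm can have an event attributed to iCBT.
- For every withdrawal, the reason and the arm.
- In section h, a descriptive table by arm, with exact confidence limits and no significance test, of participants with at least one event, withdrawals by reason, and participants whose PHQ-9, K6 or pain score was worse at week 8 than at baseline. Give the number with a week-8 score as the denominator for the last of these.

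State in section h that the table is descriptive at 20 per arm and that an absence of events is to be reported with its upper confidence limit.

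The cost is a few minutes per session, more reports of minor events, and one extra table. No added visits or staff are needed. The counts of worsening scores use data already planned.

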- **Health-Related Quality of Life-Short Form-12 (SF-12)**

This is a questionnaire consisting of twelve questions that measure eight health domains to assess physical and mental health-related quality of life (Huo et al., 2018). The reliability and validity of this questionnaire are questionable, yet it will be used in this study as it was the only short form with free access that was found (Al Sayah et al., 2013). It will be administered through an online survey.

- **Maximum Isometric Muscle Strength**

Assessing quadriceps muscle strength can indicate the individual's mobility and pain and hence it will be assessed in this study (Luc-Harkey et al., 2018). Maximal voluntary isometric quadriceps muscle strength will be assessed using a hand-held dynamometer as described by Luc-Harkey et al (2018) (Figure 4). To do the test, a participant will be seated on an examination table with their knees flexed to 60° and their feet off the ground. The hand-held dynamometer will be positioned on the anterior aspect of the distal tibia, just superior to the malleoli. An inelastic strap will be secured around the treatment table under the participant and will be used to maintain the position of the hand-held dynamometer and the knee angle during each testing trial. The participant will grasp the examination table with his/her hands for stabilization, and the participant will be instructed to extend his/her knee "as hard as possible" into the hand-

held dynamometer. The participant will continue to exert force into the hand-held dynamometer for 4 s, and the maximum force across the trial will be recorded. Three testing trials will be completed, and the average force (Newtons [N]) across the three trials will be normalized to body mass (N/kg) (Luc-Harkey et al., 2018).

f. Data Collection

Data collection points will be done at 0 and 8 weeks. In addition to the outcome measures, descriptive data will be collected at baseline by an online questionnaire. Descriptive data to be collected are age, gender, employment status, marital status, body mass index (BMI), duration of knee symptoms, previous treatments, medical history, and medications.

g. Ethical Considerations

- Ethical Approval

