point. For continuous outcomes differences in mean change will be compared between groups using linear regression random effects modelling adjusted for baseline values of the outcome. Proportional odds models will compare improvement between groups based on perceived ratings of change as well as the proportion in each group who attain the minimum clinical important difference (MCID) for pain and function. The MCID to be detected in chronic musculoskeletal trials is a change in pain of 1 unit (out of 10) (Salaffi et al., 2004). The MCID to be detected in the 30sCST and 40mFPWT are 2.0 and 0.19 respectively (Dobson et al., 2013).

- **Limitations**

This study has limitations. First, the study will be conducted with one researcher which exposes it to a risk of bias, but this risk will be minimized by blinding participants to hypotheses. Second, the determined sample size might not be reached within the study's time frame and this might affect the effect size between both groups leading to no significant results between the group. Second, some of the Arabic translated questionnaires have low reliability and/ or low validity levels, thus limiting the generalizability of their results.

Expected outcomes:

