Chronic knee pain is a debilitating condition that can affect the physical and mental health of individuals consequently compromising their quality of life. It is of great importance to address the intercorrelated physical and mental health consequences of chronic pain as this is reflected in one's wellbeing. General guidelines recommend education and exercises as core treatments. Furthermore, recommendations to incorporate CBT programs in the management of chronic knee pain are growing. Such programs are time and cost-consuming interventions. Novel methods of CBT delivery have been investigated and done with different methodologies. Many studies have been done combining exercises with an internet-based CBT. Due to the delivery mode (internet or application-based) of these studies, objective outcome measures were missed, thereby compromising the confidence in the results of these studies. In order to improve the quality of evidence, it is important to incorporate subjective and objective outcome measures. This study aims to remedy the shortcoming of missing objective outcome measures through combining a supervised face-to-face exercise program with an iCBT. In turn, this will enhance the delivery of comprehensive cost- and time-effective interventions for patients and will ensure patients' availability for objective outcome measures. Moreover, this study aims to study the effects of the combined program in patients who have certain levels of depression and psychological distress. The effectiveness of combined iCBT interventions and exercises in this specific group of individuals has not been addressed in the literature. Conducting this research will help in identifying individuals who will benefit the most of such programs and might reframe the criteria for patients to be included in these programs as they benefit the most from it.

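### Intention-to-treat is promised for participants with missing data, but the plan does not say how people who stop attending are measured at 8 weeks or how missing outcomes are handled

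*Combined protocol and SAP*

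**What the plan says.** All places are in the combined protocol and SAP.

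- **h. Data Analysis** makes intention-to-treat the main comparison and states: "This analysis will include all participants who have missing data and those who do not fully adhere to the protocol". The model for continuous outcomes is given as: "differences in mean change will be compared between groups using linear regression random effects modelling adjusted for baseline values of the outcome". On withdrawals, it plans a comparison of demographics and baseline scores: "These variables will also be examined for those participants who withdraw from the study and those who remain".
- **c. Study Procedure** fixes the follow-up occasion: "In the 8th session, self-reported questionnaires will be undertaken again as well as the objective outcome measures".
- **f. Data Collection** gives one post-baseline point: "Data collection points will be done at 0 and 8 weeks".
- **b. Participants**, exclusion 17, removes at entry anyone "Unable to comply with the protocol such as the inability to attend therapy sessions or attend assessment appointments at the health center".
- **Expected outcomes** relies on the face-to-face programme to secure patients' "availability for objective outcome measures".
- **g. Ethical Considerations** says that "participants will have the right to withdraw from the study at any stage if they wish to do so without prejudice". It does not separate stopping the sessions from refusing follow-up.

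No section describes a visit, call or form for people who have stopped attending. None names an imputation method, a missing-data assumption or a sensitivity analysis.

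**The concern.** The promise and the procedure do not meet. Including people with missing data requires either obtaining their outcome or stating how its absence is handled, and the plan does neither for someone who is not at session 8. An 8-week value that is not collected at 8 weeks cannot be recovered later. With 20 per arm, each such person is 1/20 = 5% of an arm.

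If those who stop differ from those who stay, and do so unequally between arms, the pain and function comparisons shift while the report still carries the intention-to-treat label. Unequal stopping is conceivable here. Only the study arm has the eight online CBT sessions of 35 to 45 minutes (8 × 35 = 280 to 8 × 45 = 360 minutes in all), each to be finished in the week of its physiotherapy session. That makes a difference possible; it does not show that one will occur, or in which direction.

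**Working it through.** **Inputs from the documents.** 20 per group (Sample Size); one follow-up, at 8 weeks (f. Data Collection); change adjusted for baseline (h. Data Analysis); 1 NRS point as the MCID for pain (h. Data Analysis). The 20 per group is a convenience number with no SD, power or dropout behind it, so there is no planned figure to reproduce.

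**Assumed.** All loss rates, all outcome gaps, follow-up SD 2, baseline-to-follow-up correlation 0.5.

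**Step 1: what the model uses.** With one follow-up, a person without a week-8 value has no change score. A person-level random effect cannot be separated from residual error either, so the model reduces to ordinary regression of change on group and baseline. In one simulated trial of 40 with 8 outcomes missing, the fit used 32 people and equalled the completers-only fit (difference −0.704, SE 0.453). Moving the missing people's baselines by 50 left the estimate unchanged. They contribute nothing.

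**Step 2: the shift.** Let *p* be the share of an arm not measured and *g* the number of NRS points by which those people are worse at week 8 than the measured people in their arm, at equal baseline. The arm's true mean pain is the observed mean plus *p·g*. The benefit of iCBT is therefore overstated by

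shift = p(iCBT)·g(iCBT) − p(control)·g(control).

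| Assumed case | Arithmetic | Shift (NRS points) |
|---|---|---|
| Same loss, same gap | 0.2g − 0.2g | 0 |
| 20% iCBT v 10% control (4/20 v 2/20), gap 1 to 2 in both | 0.2×1 − 0.1×1 to 0.2×2 − 0.1×2 | +0.1 to +0.2 |
| 10% iCBT v 20% control, gap 1 to 2 in both | 0.1×1 − 0.2×1 to 0.1×2 − 0.2×2 | −0.1 to −0.2 |
| 20% in both, only iCBT stoppers 1 to 2 worse | 0.2×1 − 0 to 0.2×2 − 0 | +0.2 to +0.4 |
| 20% in both, only control stoppers 1 to 2 worse | 0 − 0.2×1 to 0 − 0.2×2 | −0.2 to −0.4 |

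**Step 3: against sampling error.** The residual SD is 2 × √(1 − 0.5²) = 1.73. With 16 and 18 measured, SE = 1.73 × √(1/16 + 1/18) = 0.60; with 16 and 16, 1.73 × √(2/16) = 0.61. Simulation gave 0.60 to 0.62.

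**Step 4: can analysis repair it?** Simulation of 4,000 trials per case, with a true benefit of 1.0 in those measured, stoppers 1.5 points worse in both arms, baseline SD 1.5 and control improvement 2.0:

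| Lost (iCBT v control) | All outcomes known | Observed cases | Regression imputation from baseline, by arm | No improvement assumed for the missing |
|---|---|---|---|---|
| 4 v 2 | 0.87 (exact 1.0 − 0.1×1.5 = 0.85) | 1.02 | 1.02 | 0.62 |
| 2 v 4 | 1.14 (exact 1.15) | 0.99 | 0.99 | 1.09 |
| 4 v 4 | 1.02 (exact 1.00) | 1.02 | 1.02 | 0.81 |

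Imputing from baseline returns the observed-case answer, because it has no information on what happened after people stopped. Collecting the value is what helps.

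**The case against.** **Self-report is already largely remote.** The Outcome Measures section moves PHQ-9 and K6 to online forms after baseline and gives KOOS-PS and SF-12 as online surveys. The follow-up time is stated as 8 weeks, and exclusion 17 names assessment appointments separately from therapy sessions. This stands in part: for the questionnaires, the gap is a missing sentence and not a missing facility. But c. Study Procedure places them in session 8 and nowhere extends them to people who have left. The walk, step and chair-stand tests, three of the four primary measures, need attendance in any case.

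**Loss is already limited.** Exclusion 17 and the supervised format should reduce it. They act at entry or through attendance, so they do nothing for someone who later stops. Comparing withdrawers with remainers describes the loss and recovers no outcome.

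**The plan has not chosen an observed-case analysis.** A reader might infer that it has. The text does not say so: the method is left open, and in the MCID-attainment comparison, for example, absentees could be counted as not attaining. Observed-case is what the stated model does by default if nothing is added.

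**The effect is small.** This stands. Every loss and gap figure is assumed, and the illustrated shifts are below the sampling error.

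**Conclusion.** The concern holds as a gap between the promise and the data collection. Without an added method, the intention-to-treat label would not be met for people absent at session 8. It would be met for those who skip other sessions or the iCBT but attend session 8, so a reader who inferred that non-adherers in general drop out of the analysis would be going too far.

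The size rests wholly on assumptions: from zero up to 0.2 or 0.4 NRS points in the cases shown, against an MCID of 1 and a standard error of about 0.6 (SD 2, correlation 0.5). A reader might infer that the bias favours iCBT; the documents give no loss data, and the sign reverses with the arm affected. Nor is a larger shift confined to loss concentrated in one arm: equal 20% loss with unequal gaps gives 0.2 to 0.4. The case for change is that the remedy costs little and the values are otherwise irrecoverable, not that a large bias has been shown.

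**What to change.** 1. Amend c. Study Procedure and f. Data Collection to say: every randomised participant who has not withdrawn consent to follow-up is due an 8-week assessment, whatever sessions they completed. Keep the session-8 assessment for those attending.
2. Record stopping the sessions separately from withdrawing from follow-up.
3. At 8 weeks, send non-attenders the existing online questionnaires with the pain NRS, and invite them for the performance tests.
4. In h. Data Analysis, where values are still missing, label the comparison observed-case and report the numbers analysed per arm.
5. Optionally, add a sensitivity analysis that varies the assumed outcome of missing participants separately by arm, subtracting p(iCBT)·g(iCBT) − p(control)·g(control) over a stated range of gaps. A single no-improvement assumption applied alike to both arms does not vary the between-arm gap that drives the shift. In the simulation above it was further from the full-data value than observed cases in two of the three cases.

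Cost: a few sentences, a form link at 8 weeks, and at most one extra analysis. The downside is a little more contact work for a study that its Limitations section says is run by one researcher. Some performance-test data will still be missing, because those tests need a visit.
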